Duration of response is defined as the time from first observed response (either CR or PR, whichever comes first) until either disease progression, or death. Only subjects observed with a response shall be included in the analysis of DoR. The median DoR time and the proportion of subjects remaining with a response at 3, 6, 9, 12, 18 and 24 months, and at close of study along with the corresponding 95% CI will be calculated using Kaplan-Meier methods. Subjects who are alive and remain in disease response at the time of analysis will be censored at the time of their last adequate disease assessment or at the time of starting a new anticancer therapy, whichever is first. Due to the low number of subjects to be included in the analysis, additional summary statistics will be presented. Each stratum shall be analyzed separately. Analysis of this endpoint will be based on the ITT Population and/or Safety Population.

Progression-Free Survival

Progression-free survival is defined as the time from enrollment until either disease progression, or death of any cause, whichever occurs first. The median PFS time and proportion of subjects remaining progression-free at 3, 6, 9, 12, 18 and 24 months, and at close of study along with the corresponding 95% CI calculated using Kaplan-Meier methods will be presented. Subjects remaining progression-free at the time of analysis will be censored at the time of their last adequate disease assessment. Additionally, subjects will be censored at the time of starting a new anticancer therapy if having not had disease progression previously. Due to the low number of subjects to be included in the analysis, additional summary statistics will be presented. Each stratum shall be analyzed separately. Analysis of this endpoint will be based on the ITT Population and/or Safety Population.

Overall Survival

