Overall survival is defined as the time from enrollment until death of any cause. The median OS time and proportion of subjects remaining alive at 3, 6, 9, 12, 18 and 24 months, and at close of study, along with the corresponding 95% CI, calculated using Kaplan-Meier methods will be presented. Subjects remaining alive at the time of analysis will be censored at the time they were last known to be alive. Due to the low number of subjects to be included in the analysis, additional summary statistics will be presented. Each stratum shall be analyzed separately. Analysis of this endpoint will be based on the ITT Population and/or Safety Population.

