6.2.4. Progression-free Survival

Progression-free survival (PFS) will be presented in weeks and is defined as the time from the date of first pomalidomide dose until the date a PD is first observed or date of death (any cause), whichever occurs first. Subjects who do not have a PD or have not died at the time of an analysis will be censored at the time of their last disease assessment or at the time of start of new anticancer therapy, whichever occurs first.

For the purpose of identification of a PD for this endpoint, PD is classified as either a PD as observed during a response assessments (both during the Treatment Period and the Follow-up Period if applicable), or as a PD as recorded on the Disposition – Treatment and/or the Disposition – Follow-up eCRF; the first time this occurrence is observed is selected as the PD date.

Progression-free survival will be summarized by median progression-free time along with the corresponding 95% CI, calculated using Kaplan-Meier methods (the estimate of variance will be calculated using Greenwood's formula) ([Kaplan and Meier, 1958](#)) for each tumor type/disease indication separately. The Kaplan-Meier curves for PFS will be presented graphically. The number and percentage of total disease progression/deaths, as identified for PFS events will be summarized. The proportion remaining progression/death free at 3, 6, 9, 12, 18, and 24 months will be reported and the corresponding standard error provided.

Due to the low anticipated number of subjects and events/censoring, additional summary statistics will be provided, including the arithmetic mean, median, StdDev, Q1, Q3, Min, and Max values.

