6.2.5. Overall Survival

Overall survival (OS) will be presented in months and is defined as the duration in months from the date of first pomalidomide dose to the date of death (any cause). Subjects who are alive at the time of analysis will be censored at the last known time that the subject was alive. Overall survival will be summarized by median survival time along with the corresponding 95% CI, calculated using Kaplan-Meier methods (the estimate of variance will be calculated using Greenwood's formula) ([Kaplan and Meier, 1958](#)) for each tumor type/disease indication separately. The Kaplan-Meier curve for survival will be presented graphically. The number and percentage of total deaths will be summarized. The survival rate at 3, 6, 9, 12, 18, and 24 months will be reported and the corresponding standard error provided.

Due to the low anticipated number of subjects and events/censoring, additional summary statistics will be provided, including the arithmetic mean, median, StdDev, Q1, Q3, Min, and Max values.

In addition to presentation of OS analysis data, descriptive statistics (arithmetic mean, median, StdDev, Q1, Q3, Min, and Max values) for follow-up time shall be presented for all subjects regardless of survival status, and for only subjects alive at the time of the analysis. Follow-up is defined as the duration in months from the date of first pomalidomide dose to the date of death (any cause), or last known time the subject was known to be alive if alive at the time of analysis or lost to follow-up. Analyses will be based on the ITT Population and/or Safety Population. The ITT Population will not be used should all enrolled subjects have received at least one dose of study drug.

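### SAP 6.2.3 to 6.2.5 give landmark DoR, PFS and OS rates with a standard error only, where Protocol 9.6 specifies 95% CIs, and omit the close-of-study rate

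*SAP*

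**What the plan says.** Protocol 9.6 treats the three time-to-event endpoints alike. For PFS it lists the median and the proportions at six landmarks, then continues "and at close of study along with the corresponding 95% CI calculated using Kaplan-Meier methods will be presented". The DoR paragraph has "and at close of study along with the corresponding 95% CI will be calculated using Kaplan-Meier methods", and the OS paragraph has "and at close of study, along with the corresponding 95% CI, calculated using Kaplan-Meier methods will be presented".

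The SAP divides this differently. In 6.2.4 the interval belongs to the median: "Progression-free survival will be summarized by median progression-free time along with the corresponding 95% CI, calculated using Kaplan-Meier methods", with Greenwood's formula named for the variance. The landmarks get something else: the six proportions "will be reported and the corresponding standard error provided". SAP 6.2.3 uses the same sentence for DoR. SAP 6.2.5 has the parallel one for OS: "The survival rate at 3, 6, 9, 12, 18, and 24 months will be reported and the corresponding standard error provided".

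None of the three SAP sections lists a close-of-study rate or gives a reason for the change. None says on what scale limits would be formed if anyone wanted them. Appendix A1 fixes the level and sidedness of any CI that is shown, but does not call for one at the landmarks.

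**The concern.** The SAP is the document the programmers follow, so outputs specified this way would lack an interval that the protocol promises for three secondary endpoints. The gap stands out because the SAP uses Clopper-Pearson limits, which suit small samples, for ORSDR, ORR and the long-term SD rate.

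What is at stake is how a reader judges the precision of a rate from a very small group. The usual shortcut with an estimate and a standard error is to add and subtract 1.96 standard errors. That works badly for small samples when the rate is near 0 or 1, and low rates are plausible here. Protocol 1.1.1 describes poor outcomes after recurrence and a median PFS of 4.5 months from diagnosis for DIPG. As an illustration only, an exponential curve with that median would give 0.5^(9/4.5) = 25% at 9 months and 0.5^(18/4.5) = 6.25% at 18 months.

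**Working it through.** **Inputs.** Protocol 9.3 gives 9 evaluable subjects per stratum in Stage 1 and 20 in total. SAP 6.2.3 to 6.2.5 name Greenwood variance. SAP 6.2.3 confines DoR to responders.

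**The plan's own figure.** The SAP states no precision for the landmark rates, so the figure to reproduce is the sample size. An exact search for Simon's optimal design (10% versus 40%, 5% level, 90% power) returns 9 then 20 subjects, continuing with at least 2 of 9 and positive with at least 5 of 20. Attained alpha is 0.0349 and power 0.9018. The sizes 9 and 20 are therefore as the plan states.

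**Formulas, assuming no censoring before the landmark.**
- Greenwood standard error: SE = sqrt(S(1−S)/n).
- Plain limits: S ± 1.96·SE.
- Log-log limits: S^exp(±1.96·SE/(S·|ln S|)).

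| Event-free | Rate | SE | Plain 95% limits | Log-log 95% limits |
|---|---|---|---|---|
| 1/9 | 11.1% | 10.5% | −9.4% to 31.6% | 0.6% to 38.8% |
| 2/9 | 22.2% | 13.9% | −4.9% to 49.4% | 3.4% to 51.3% |
| 3/9 | 33.3% | 15.7% | 2.5% to 64.1% | 7.8% to 62.3% |
| 8/9 | 88.9% | 10.5% | 68.4% to 109.4% | 43.3% to 98.4% |
| 2/20 | 10.0% | 6.7% | −3.1% to 23.1% | 1.7% to 27.2% |
| 3/20 | 15.0% | 8.0% | −0.6% to 30.6% | 3.7% to 33.5% |
| 4/20 | 20.0% | 8.9% | 2.5% to 37.5% | 6.2% to 39.3% |
| 18/20 | 90.0% | 6.7% | 76.9% to 103.1% | 65.6% to 97.4% |

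**Where plain limits fail.** For 0 < S < 1, the lower limit is negative when S < z²/(n+z²), and the upper limit exceeds 1 when S > n/(n+z²), with z² = 3.84.
- n=9: 3.84/12.84 = 29.9% and 9/12.84 = 70.1%. The affected counts are 1, 2, 7 and 8, which is 4 of the 10 possible.
- n=20: 3.84/23.84 = 16.1% and 20/23.84 = 83.9%. The affected counts are 1 to 3 and 17 to 19, which is 6 of the 21 possible.

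**At 0% or 100%.** The SE is 0, so the plain interval has no width, and the log-log interval is undefined. The exact (Clopper-Pearson) upper limit for zero events-free is 1 − 0.025^(1/n): 33.6% for 0/9 and 16.8% for 0/20.

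**DoR.** With 2, 3 or 5 responders, every rate strictly between 0 and 1 gives an impossible plain limit. Examples are 1/2 (−19.3% to 119.3%), 1/3 (−20.0% to 86.7%) and 2/5 (−2.9% to 82.9%).

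**The case against.** The strongest reply is that nothing wrong has been specified. A standard error is not an interval, and the SAP nowhere says it will form plain limits. A reader might infer that the SAP will produce impossible limits, or that its standard error can only be turned into a symmetric interval. Neither is supported. The rate and its standard error are enough for a log-log interval: for 1/9, 0.105/(0.111 × 2.197) = 0.429 on the transformed scale, which gives the 0.6% to 38.8% shown above. The information is lost only at 0% or 100%. Plain limits also stay inside 0-100% for 3/9 to 6/9 and for 4/20 to 16/20.

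A reader might also infer that these rates will drive a later development decision. The documents do not say so. Go/no-go rests on ORSDR (Protocol 9.3, SAP 6), no historical PFS or OS benchmark is set, and these endpoints are described without a test.

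Finally, it could be said that SAP 12 covers close of study, because all outputs are rerun once follow-up ends. That rerun repeats the specified outputs; it does not add a close-of-study proportion to the six landmarks.

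These replies limit the size of the point. They do not remove the mismatch: the protocol specifies an interval at each landmark, and the SAP neither provides it nor explains why.

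**Conclusion.** The point holds as a protocol-SAP discrepancy with a modest statistical consequence. For DoR, PFS and OS the SAP drops the landmark 95% CIs and the close-of-study rate. A reader who builds plain limits from the standard error will be misled at low or high rates, roughly the outer 30% of the scale on each side at n=9 and the outer 16% at n=20. At 0% or 100% a standard error of zero suggests certainty that the data do not give. DoR is affected most.

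The thresholds assume no censoring before the landmark. Censoring enlarges the Greenwood standard error and widens the affected range. They also take the evaluable numbers as n; the ITT or Safety sets used for these endpoints could be larger if subjects are replaced, which would narrow it.

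The primary endpoint, its exact interval and the stage decisions do not change. The choice of the log-log scale is a recommendation: the protocol asks only for Kaplan-Meier methods and names no transformation.

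**What to change.** In SAP 6.2.3, 6.2.4 and 6.2.5:

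- Add a two-sided 95% CI for the Kaplan-Meier estimate at each of the six landmarks, on the log-log scale with Greenwood variance. The standard error can stay beside it.
- State a rule for estimates of 0% or 100%. For example, give an exact Clopper-Pearson limit when no subject was censored before that landmark; otherwise show the limit as not estimable, with the number at risk.
- Restore the close-of-study rate with its CI, or say why it was removed.

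The cost is one option in the Kaplan-Meier procedure, a short rule for the boundary cases and a small SAP revision before database lock. No new data, visits or subjects are needed.

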6.2.3. Duration of Response

Duration of response (DoR) will be presented in weeks is defined as the duration from initial response (either a CR or PR) to documented PD or death due to any cause, whichever occurs first. The response criteria should be defined in the protocol prior to the start of the study. Duration of response for subjects last known to be alive without PD is censored at the date of last adequate response assessment, or at the start of a new anticancer therapy, whichever occurs first.

The underlying analysis population is confined to those who have responded.

For identification of PD for this endpoint, PD is classified as either a PD as observed during a response assessments (both during the Treatment Period and the Follow-up Period if applicable), or as a PD as recorded on the treatment discontinuation and/or the study discontinuation eCRF; the first time this occurrence is observed is selected as the PD date.

Duration of response will be summarized by median DoR time, along with the corresponding 95% CI, calculated using Kaplan-Meier methods (the estimate of variance will be calculated using Greenwood's formula) ([Kaplan and Meier, 1958](#)) for each tumor type/disease indication separately. The Kaplan-Meier curve for DoR will be presented graphically. The proportion remaining progression/death free at 3, 6, 9, 12, 18, and 24 months will be reported and the corresponding standard error provided.

Due to the low anticipated number of subjects and events/censoring, additional summary statistics will be provided, including the arithmetic mean, median, standard deviation (StdDev), first quartile (Q1), third quartile (Q3), minimum (Min), and maximum (Max) values.

Disease assessments recorded on or after start of a new anticancer therapy will not be considered, nor will disease assessments reported after a PD has been observed.

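### SAP 6.2.3 to 6.2.5 add a plain mean, median, standard deviation and quartiles for DoR, PFS and OS with no rule for censored times; once censoring occurs these run low and often disagree with the Kaplan-Meier median

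*SAP*

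**What the plan says.** SAP 6.2.3 (DoR), 6.2.4 (PFS) and 6.2.5 (OS) share one structure. Each first gives the standard estimator. For PFS: "Progression-free survival will be summarized by median progression-free time along with the corresponding 95% CI, calculated using Kaplan-Meier methods". Curves and rates from 3 to 24 months follow.

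Each has a censoring rule. DoR without progression or death is "censored at the date of last adequate response assessment, or at the start of a new anticancer therapy, whichever occurs first". PFS subjects without an event "will be censored at the time of their last disease assessment or at the time of start of new anticancer therapy, whichever occurs first". For OS: "Subjects who are alive at the time of analysis will be censored at the last known time that the subject was alive".

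Each section then adds a second set of figures, for a stated reason: "Due to the low anticipated number of subjects and events/censoring, additional summary statistics will be provided". In 6.2.4 the sentence continues: "additional summary statistics will be provided, including the arithmetic mean, median, StdDev, Q1, Q3, Min, and Max values". The DoR and OS sections carry the same list.

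None of the three sections says whether the extra figures use all times, events only, or Kaplan-Meier quantiles. Protocol 9.6 foresees extra summary statistics for these endpoints but does not name them.

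SAP 6.2.5 separately plans descriptive statistics "for follow-up time shall be presented for all subjects regardless of survival status, and for only subjects alive at the time of the analysis".

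**The concern.** A censored time is a lower bound on the time of interest. An arithmetic mean, standard deviation or sample quartile has no place for that information, so some choice about censored records has to be made, and the SAP makes none.

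The wording points to plain descriptive statistics. A Kaplan-Meier median is already specified, so a second median is redundant unless it is computed differently. Appendix A1 gives the same list as the ordinary layout for continuous variables, with no censoring flag. SAP 6.2.5 applies the list to follow-up time, which it defines as first dose to death or last known alive. That is the OS time without its event indicator. If the extra OS figures cover all subjects, they repeat the all-subject follow-up table under a survival label.

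At stake is the secondary objective of estimating long-term efficacy. There is no control arm, so the absolute figures are what readers will take away. Two medians for one endpoint in one report invite misquotation.

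Censoring is plausible. PFS and DoR are cut at new anticancer therapy. The primary final analysis (SAP 12) follows the last 28-day safety visit, while survival follow-up can continue to 5 years after the last enrolment.

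**Working it through.** **Plan's own figures.** The plan states no number on this point. The stratum sizes used below, 9 after Stage 1 and 20 in total, come from Protocol 9.3 and SAP 4.4. That design reproduces exactly (continue on at least 2/9, positive on at least 5/20: alpha 0.0349, power 0.9018) and is not in dispute.

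**Direction.** Let T be the event time and C the censoring time.

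- *All times.* The observed time is min(T, C), which never exceeds T. The mean and every ordered value are therefore at or below what full follow-up would give.
- *Events only.* With independent censoring, observed events have density proportional to f(t) × P(C ≥ t), which favours short times. The result is again low.

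**Size, under an assumption.** Take exponential T with rate λ and independent exponential C with rate μ.

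- Censored share: c = μ / (λ + μ), so λ + μ = λ / (1 − c).
- min(T, C) is exponential with rate λ + μ. Its median and mean are (1 − c) times the true values.
- In this model the observed time is independent of whether it is an event, so the events-only distribution is the same.

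Example with assumed values: a true median of 6 months and 40% censored gives (1 − 0.4) × 6 = 3.6 months.

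**Check at the trial's stratum sizes.** There were 5,000 simulated strata per cell, with true median 1.00 and true mean 1 / ln 2 = 1.44. Medians are typical (median) values across strata. Plain figures count all times.

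| Censored | KM median n=9 / n=20 | Plain median n=9 / n=20 | Plain mean n=9 / n=20 | Strata where the two medians differ n=9 / n=20 |
|---|---|---|---|---|
| 0% | 1.00 / 0.93 | 1.00 / 0.93 | 1.44 / 1.43 | 0% / 0% |
| 10% | 1.00 / 0.97 | 0.89 / 0.85 | 1.29 / 1.30 | 33.6% / 64.6% |
| 20% | 1.00 / 0.99 | 0.80 / 0.75 | 1.15 / 1.16 | 58.7% / 89.7% |
| 30% | 1.00 / 1.00 | 0.69 / 0.66 | 1.01 / 1.01 | 76.5% / 97.5% |
| 40% | 1.00 / 0.99 | 0.61 / 0.56 | 0.87 / 0.86 | 86.9% / 99.5% |
| 50% | 1.01 / 0.99 | 0.49 / 0.46 | 0.73 / 0.72 | 93.7% / 99.8% |

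The last column counts an unreached Kaplan-Meier median as a difference; at 50% censoring that is 10.5% of strata at n=9 and 2.4% at n=20. The 0.93 at n=20 without censoring comes from taking the 10th of 20 ordered times as the median, not from censoring. Relative to 0.93, the n=20 plain medians are 0.91, 0.81, 0.71, 0.60 and 0.49.

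Events-only means agree with the all-times means to within 0.01. Events-only medians are 0.87, 0.76, 0.67, 0.56, 0.46 at n=20 and 0.83, 0.72, 0.62, 0.53, 0.42 at n=9, for 10% to 50% censoring.

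**Invented nine-subject example** (+ marks censored): 4, 6+, 8, 8.5+, 12, 16+, 20, 24, 30+.

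- Kaplan-Meier: 8/9 = 0.889 at 4; × 6/7 = 0.762 at 8; × 4/5 = 0.610 at 12; × 2/3 = 0.406 at 20. The median is 20.
- All times: median 12, mean 128.5 / 9 = 14.3.
- Events only (4, 8, 12, 20, 24): median 12, mean 68 / 5 = 13.6.

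**The case against.** The strongest reply is that the SAP nowhere says censored times are handled as events. A reader might infer that from the word arithmetic and from the list itself, but the text does not state it, and events only is an equally open reading. This stands, so the defect is a missing rule. It does not rescue the figures, because both plain readings run low.

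A reader might also infer that the SAP expects heavy censoring, or that the reports are bound to show two different medians. Neither follows. In the stated reason, low can be read as covering events and censoring as well as subjects. Without censoring the two medians coincide, and at 10% censoring with nine subjects they differ in only about a third of simulated strata. SAP 12 also reruns all outputs at the end of follow-up, when OS should be more mature.

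The Kaplan-Meier medians, curves and landmark rates remain in the plan. PFS events and deaths are already counted in 6.2.4 and 6.2.5. The extra figures are labelled additional. All of this stands and limits the harm, but a second median that is biased once times are censored does not become useful by sitting beside a sound one.

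Minimum and maximum are worth keeping, particularly for DoR, where responders may be few and a Kaplan-Meier median may not be estimable. The follow-up summary in 6.2.5 is clearly defined, names the subjects included, and is not at fault.

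**Conclusion.** The point holds as a gap with a predictable consequence. SAP 6.2.3 to 6.2.5 add a mean, median, standard deviation and quartiles for censored endpoints with no rule for censored times. On either plain reading the mean, median and quartiles are biased low when censoring occurs.

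The size, about 10% to 50% low for 10% to 50% censoring, rests on assumed exponential times and independent exponential censoring. The documents give no censoring rate, so it is a range and not a forecast for this trial; other censoring patterns would change the amount. The n=9 and n=20 results speak to PFS and OS. DoR uses responders only, so its numbers will be smaller.

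A reader might infer that the efficacy conclusions are in doubt. They are not: continuation to Stage 2 and the final declaration in each tumor type rest on ORSDR in the Response Population (SAP 4.4, 6 and 6.5), which uses none of these statistics. The effect is confined to descriptive outputs for secondary endpoints.

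**What to change.** In SAP 6.2.3, 6.2.4 and 6.2.5:

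- replace the plain mean, median, standard deviation and both quartiles with Kaplan-Meier quartiles and their 95% CIs, stated as not estimable where they are not reached;
- keep the minimum and maximum, flagging any value that is censored;
- report the number of events and of censored subjects for each endpoint (6.2.4 and 6.2.5 already count events; 6.2.3 does not);
- if a mean is wanted, use a restricted mean to a horizon stated in the SAP.

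Leave the follow-up-time summary in 6.2.5 as it is.

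The cost is SAP wording and small changes to three table shells. No new data are needed, and no protocol amendment, because Protocol 9.6 does not name the additional statistics.
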